6.3 PATIENTS SETS ANALYSED

The following analysis sets will be defined for this trial:

- Enrolled set (ENR)

This patient set includes all patients with informed consent given. The enrolled set will be used for patient disposition tables.

- Treated set (TS)

This patient set includes all patients who are documented to have received and taken at least one dose of any study medication during the treatment cycles (including run-in period).

The TS will be used for all planned safety and efficacy analyses.

- MTD Set (MS)

The MTD set defines the set of patients in the dose-finding cohorts (cohorts A,B,C and D) of the trial that are fully evaluable for determination of the MTD in the first treatment course. The MTD set will be used for some safety analyses for dose-finding cohorts, this is specified in the technical TSAP.

[figure not shown]
Patients in the TS who were replaced within the MTD period in the dose-finding cohorts (cohorts A,B,C and D) of the trial will be excluded from the determination of the MTD. Patients in the TS who entered in an expansion cohorts will be also excluded from the determination of the MTD. Replacement of patients in the dose-finding cohorts of the study is defined in Section 3.3.5 of the CTP. The final list of replaced patients is supplied by the Clinical Trial Leader (CTL) no later than the last report planning meeting before the database lock for the safety analysis.

- Pharmacokinetic set (PKS)

Proprietary confidential information © 2021 Boehringer Ingelheim International GmbH or one or more of its affiliated companies

This patient set includes all patients in the treated set who have at least one valid drug plasma concentration available. The decision whether a concentration is considered valid or not will in general be made at the RPM before Database Lock (DBL) or URPM and documented within the respective meeting minutes. Values to be excluded from analyses identified during analysis would be documented within the respective QC forms. The PKS will be used for the PK analyses of the trial.

No per protocol population will be used for analyses.

6.5 POOLING OF CENTRES

This section is not applicable because there are no inferential statistics, and therefore there is no statistical model in which centre/country can be included.

6.6 HANDLING OF MISSING DATA AND OUTLIERS

In general, missing data will not be imputed, unless required for the following analyses and definitions. Then the rules as described below apply.

Missing dates that affect the evaluation of endpoints specified in previous sections of this TSAP will be imputed utilising a “worst case” approach, which will be applied on a case-by-case basis (depending on the affected endpoint) and agreed to by the trial team members at the final BRPM before database lock at the latest.

The rules in the [Table 6.6: 1](#) below have been agreed by the trial and project teams, and will be used in this trial, if applicable.

Table 6.6: 1 Rules for imputations of missing or incomplete dates

Date	Imputation rule
Date of birth	In case only the year is given: 1 st of January
Date of death	Date last known to be alive. If only year and month are given: this will be imputed with 1 st of the month for the analysis of OS
Date of first histological diagnosis	1 st of month if day is missing 1 st of January if month also missing
Date of first appearance or recurrence of metastasis	1 st of month if day is missing 1 st of January if month also missing
Date of start of concomitant medication	No imputation required

Proprietary confidential information © 2021 Boehringer Ingelheim International GmbH or one or more of its affiliated companies

Date of end of concomitant medication	No imputation required
Date of start of subsequent anti-cancer therapy (imputation required only for censoring of PFS)	If the day (respectively day and month) of the start date of subsequent anti-cancer therapy is missing, then the first of the month (respectively 1st January) will be imputed unless this date leads to a date before the stop date of study medications. In this case, the study medications stop date + 1 day will be imputed. Additionally, all imputed start dates of subsequent anti-cancer therapy should be before death date if available.
Date of end of treatment (only for patients still ongoing at time of snapshot/interim DBL)	Date of snapshot If date of death before this date, use date of death

6.6.1 Adverse events

Missing or incomplete AE dates are imputed according to BI standards ([5](#)).

6.6.2 Laboratory values at baseline

For missing laboratory data at Cycle 1 Visit 1 of Cohort A, B, C, D, D1, D2 and F or at Day 1 Run-in period of Cohort E (before the very first administration of study medication) data from preceding visits will be used.

6.6.3 PK parameters

Missing data and outliers of PK data are handled according to BI standards ([2](#)) and as described in Section 7.5 of the clinical trial protocol.

6.7 BASELINE, TIME WINDOWS, AND CALCULATED VISITS

6.7.1 Baseline

The last measurement observed prior to start of trial medication will be assigned to baseline. Note that for some trial procedures (for example body weight, vital signs, laboratory tests) this may be the value measured on the same day trial medication was started. In these cases it will be assumed that the measurements were taken prior to the intake of any study medication. For tumour assessment, baseline evaluations must be based on Magnetic Resonance Imaging (MRI) or Computed Tomography scans performed no more than 28 days prior to start of trial medication.

Study days and visits will be labelled according to the flow chart of the CTP.

Unless otherwise specified, baseline is defined as the latest time-point before the very first administration of any study medication. The run-in period in Cohort E is considered as time with study medication. If this criterion is not fulfilled then no baseline will be derived .

Laboratory values:

Proprietary confidential information © 2021 Boehringer Ingelheim International GmbH or one or more of its affiliated companies

Baseline is defined as the latest time-point before the very first administration of any study medication.

If any of these times are missing and the date of laboratory value is equal to the date of first study drug administration, then the laboratory assessment will be considered as according to protocol, i.e. as prior to first study medication.

6.7.2 Time windows for every RECIST assessment

In order to identify whether consecutive imaging time-points are missing for a given patient, a nominal time point [8, 16, 24, 32, 40, 48, 60 weeks and every 12 weeks thereafter] will be assigned to each and every image. This is achieved by creating windows for every RECIST assessment. The windows are defined in [Table 6.7.2: 1](#) below. Day 1 corresponds to the date of first drug intake of any trial medication (excluding run-in period).

Table 6.7.2: 1 Nominal time-points and windows for imaging

Nominal time-point [weeks from start of therapy]	Due date of scans [days]	Window [days]
8	57	1 to =< 85
16	113	86 to =< 141
24	169	142 to =< 197
32	225	198 to =< 253
40	281	254 to =< 309
48	337	310 to =< 379
60	421	380 to =< 463
every 12 week interval	etc [1]	etc [1]

[1] Due date of imaging = (nominal time point * 7) + 1. To calculate the lower bound of the window, use the middle point between the due date of the previous time point and the current due date + 1. To calculate the upper bound of the window, use the middle point between the due date of the next time point and the current due date.

If a patient does not have an image in one of the windows described above, he/she will be said to have 'missed an assessment' for that time-point. In case a patient has more than one assessment in one window, the assessment with the latest outcome will be used for the analysis unless a PD has been recorded earlier then PD will be used.

7 PLANNED ANALYSES

The labelling and display format of statistical parameters will follow BI standards (9).

Unless otherwise specified, outputs will be displayed separately for each cohort of the trial.

Descriptive statistics for continuous variables will generally contain N (number of patients in that patient set with non-missing values), Mean, Standard Deviation, Minimum (Min), Q1 (25th percentile), Median, Q3 (75th percentile), Maximum (Max). In general, means, standard deviations, medians, Q1 and Q3 will be presented to one more decimal place than the raw data. Minima and maxima will be presented to the same number of decimal places as the raw data.

For time-to-event analysis tables, the set of statistics is: number of patients [N (%)], Number of patients with event [N (%)], Number of patients censored [N (%)], <Time to event> [months] followed by P25 (25th percentile), Median, P75 (75th percentile). If not specified otherwise, the duration as well as time to event will be displayed in months.

Tabulations of frequencies for categorical data will include all possible categories and will display the number of observations in a category as well as the percentage (%) relative to the respective treatment group total. Percentages will be rounded to one decimal place.

In general a category “missing” will be displayed, if there are missing data for the corresponding variable. Percentages will also generally be based on all patients in the respective patient set whether they have non-missing values or not.

Sort order for general categorical variables: If categories correspond to the collected categories on the eCRF and the table shells do not explicitly specify the ordering, the “default ordering” defined by the eCRF is to be used in such cases. If categories are derived the ordering as specified in the table shell document should be used; in general ordinal data (e.g. categorised continuous data) are to be displayed in ascending order.

The denominator of the main categories is defined by the number of patients in the used patient set. The main categories define the denominators of the subcategories. Subcategories should be indented and “[N (%)]” to be displayed only for the main category.

If a table includes only categorical data, “[N (%)]” is to be displayed in the column header.

In general, a “Total” column will not be displayed for post-baseline displays. Tables that display the status of patients for a primary or secondary endpoint with number of events and number censored will contain a total column.

Abbreviations (e.g., Wors.) or acronyms (e.g., PD) should not be displayed in tables and patients data listings without any explanation. They will be either spelled out in the table or explained in footnotes (whatever is more reasonable from the programming point of view).

If applicable, conversion from days to weeks, months and years will be as follows:

- Weeks = days ÷ 7
- Months = days × 12 ÷ 365.25
- Years = days ÷ 365.25

Proprietary confidential information © 2021 Boehringer Ingelheim International GmbH or one or more of its affiliated companies

7.1 DEMOGRAPHIC AND OTHER BASELINE CHARACTERISTICS

Only descriptive statistics are planned for this section of the report.

7.1.1 Disposition of patients

For patient disposition the standard descriptive table from the EOT catalogue will be populated. Additionally, patients with discontinuations by initial treatment and the reasons will be listed and tabulated, overall and for each treatment separately. The same output will also contain an overview of discontinued and non-discontinued, as well as completed and non-completed patients (see CTP Section 6.2.3.3).

7.1.2 Important protocol deviations

A table and a listing of patients with important protocol deviations based on [Table 6.2: 1](#) will be created in Section 10.1.3 and Appendices 10.10.3 respectively, of the CTR.

7.1.3 Demographic and other baseline characteristics

Standard descriptive analysis and summary tables for all patients treated by initial treatment will be created for demographic data, oncological history and baseline conditions.

7.2 CONCOMITANT DISEASES AND MEDICATION

Only descriptive statistics are planned for this section of the report. Concomitant diseases will be coded similarly as adverse events based on the most current Medical Dictionary for Regulatory Activities (MedDRA) version. Concomitant therapies will be coded according to World Health Organisation - Drug Dictionary (WHO-DD). Concomitant therapies (CT) will be classified according to the Anatomical, Therapeutic, Chemical (ATC) classification system. The third ATC level will be used to categorise CTs by therapy type. In situations where a medical product may be used for more than one equally important indication, there are often several classification alternatives. As appropriate, patients receiving CTs with more than one possible ATC level-three category will be counted more than once; footnotes will clarify this possible double counting in tables.

Concomitant medications will be presented according to whether they are concomitant with the reception of study medication, or whether they were given prior to study medication. In case start and stop dates of the medications are completely missing, they are assigned as given prior to study medication.

7.3 TREATMENT COMPLIANCE

Compliance will not be analysed separately, but assessed in terms of exposure (including dose intensity). Refer to [Section 7.7](#) for further details on exposure analysis.

7.4 PRIMARY ENDPOINTS

7.4.1 Cohorts A, B, C, and D

The primary endpoints are the MTD and the occurrence of DLT. The MTD is determined from the occurrences of DLTs during the MTD evaluation period (this period is defined in

Proprietary confidential information © 2021 Boehringer Ingelheim International GmbH or one or more of its affiliated companies

[Section 5.1.1](#)). An overall summary of the DLTs (see CTP Section 5.3.7 for definitions of DLT) which occurred during the MTD evaluation period and the on-treatment period will be provided for each dose cohort.

Patients that were treated but replaced for the MTD evaluation (see CTP Section 3.3.5) will be excluded from the MTD determination. Replacement of patients will be determined on a case by case basis; exclusion of these patients from the MTD evaluation will be confirmed by the trial team at the report planning meeting prior to database lock.

The analysis of the MTD is based on a BLRM guided by the escalation with overdose control principle. The MTD is defined as the highest dose for a given schedule that is expected to cause less than 25% risk of the true DLT rate being above or equal to 33% during the MTD evaluation period. Estimation of the MTD during the dose escalation phase of the study will be based upon the estimation of the posterior probability of the incidence of DLT in toxicity categories during the MTD evaluation period for all evaluable patients. The model to be used is specified in CTP Section 7.

The posterior probabilities that the toxicity rates of each dose level fall into the categories specified in CTP Section 7 will be displayed.

At the end of each dose finding cohort, a safety analysis will be performed to determine the RP2D. The results will be documented for internal use and communication with the participating investigators (see also in [Section 9.1](#)).

7.4.2 Cohort E

Objective response (OR)

OR as assessed by investigators is defined as a best overall response of CR or PR and will be analysed. Descriptive statistics including number of treated patients, number of patients with objective response as best overall response and the corresponding percentages will be presented and evaluated.

7.4.3 Cohorts D1 and D2

PFS status at 18th month (PFS18)

PFS18 is defined as the PFS status of a patient who is alive without disease progression at 18 months after first treatment administration, where progression is determined according to RECIST 1.1.

Descriptive statistics including number of treated patients, number of patients being absence of disease progression or death at 18th month and the corresponding percentages will be presented and evaluated.

Kaplan-Meier (KM) estimates will be used to display the distribution of PFS for cohort D1 and D2 separately on a KM curve. To support the plot, estimated survival probabilities at specific time points of interest (6 months, 12 months and 18 months) will be tabulated. In addition, the survival distribution will be used to provide estimates of the median, 25th and 75th percentiles.

Proprietary confidential information © 2021 Boehringer Ingelheim International GmbH or one or more of its affiliated companies

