The primary endpoint of the expansion cohorts is Objective Response (OR) or PFS rate, which is a well-accepted endpoint for such studies. OR rate defined as the proportion of patients with tumor size reduction of a predefined amount and for a minimum time period is used as primary endpoint for cohort E and F. PFS18 defined as the proportion of patients who were absence of disease progression or death at 18th month is use as primary endpoint for cohorts D1 and D2. A good response of sufficient duration is reasonably likely surrogate for clinical benefit in refractory solid tumour indications or where there is no effective therapy.

PK assessments in the dose escalation cohorts (A, B, C, D (dose finding)) will be limited to the assessment of immunogenicity (anti-drug antibodies ADA) together with a concomitant PK sample for xentuzumab. The basic PK properties of each of the components have been described already.

The potential development of ADAs (immunogenicity against xentuzumab) will be monitored in all patients throughout the trial duration and beyond this (at EOTV and FUV). Regulatory guidelines recommend the monitoring of immunogenicity before, during and beyond treatment. A concomitant PK sample is necessary in order to assess whether an ADA sample result is conclusive or not and to monitor whether any effects of potential ADAs affect the drug concentration.

According to guidelines, combination therapies in oncology should be assessed for their potential effects on the exposure of each other. Therefore, PK investigations of the combination therapies in the trial will be conducted in the expansion cohort E for abemaciclib with xentuzumab and in the expansion cohorts D1 and D2 for fulvestrant with xentuzumab in an exploratory fashion. This approach ensures that a certain number of patients, treated at the same dose, can be evaluated. An intraindividual assessment of the PK of abemaciclib with and without xentuzumab treatment is planned for cohort E. These investigations are performed when the drug to be investigated is at steady state. In order to reach steady state levels with the

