7.3.1 Primary endpoint analyses

For dose finding cohorts A, B, C, and D (dose finding):

In order to identify the MTD, the number of patients with DLTs during the MTD evaluation period at each dose level will be presented. Patients who discontinue during the first treatment course for reasons other than DLT will be excluded from the determination of MTD.

For expansion cohort E:

Objective response will be analysed in terms of objective response rate, defined as the proportion of patients with best overall response of CR or PR (note that no confirmation is required for best overall response).

For cohorts D1 and D2:

PFS rate at 18th month will be derived using Kaplan Meier method. Cohort D1 for visceral vs. cohort D2 for non-visceral will be displayed separately. The details will be described in the TSAP.

For expansion cohort F

DC will be analysed in terms of DC rate, defined as the proportion of patients with best overall response of CR, PR, SD lasting for at least 24 weeks or non-CR/non-PD lasting for at least 24 weeks.

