5.1.3 Cohorts D1 and D2

The primary endpoint for expansion part cohort D1 and D2 is Progression-free survival (PFS) status at 18th month (PFS18).

PFS18 is defined as the PFS status of a patient who is alive without disease progression at 18 months after first treatment administration, where progression is determined according to RECIST 1.1.

PFS is defined as the time from first treatment administration until tumour progression according to RECIST 1.1 or death from any cause, whichever occurs earlier.

Tumour assessments will be performed at screening and then every 8 weeks after start of the first treatment course until week 48 and every 12 weeks thereafter.

For each follow-up imaging time-point an overall tumour response will be determined according to RECIST 1.1. The overall tumour response for each imaging time-point will be selected from the following categories: Complete Response (CR); Partial Response (PR); Stable Disease (SD); Progressive Disease (PD); Non-CR/Non-PD; or Not Evaluable (NE).

For details on the imaging process and RECIST evaluation, see Section 5.2 and Section 10.4 of the CTP.

Derivation of endpoint PFS

Derivations below are described in days. However, the endpoints below will be presented in months in the statistical tables produced for the Clinical Trial Report (CTR).

Proprietary confidential information © 2021 Boehringer Ingelheim International GmbH or one or more of its affiliated companies

For patients with 'event' as an outcome for PFS: (according to RECIST version 1.1)

- PFS [days] = date of outcome - date of the first treatment administration + 1.

For patients with 'censored' as an outcome for PFS: (according to RECIST version 1.1)

- PFS (censored) [days] = date of outcome - date of the first treatment administration + 1.

The censoring rules for PFS (i.e. outcome and date of outcome) are given in [Table 5.1.3:1](#). Clinical disease progression will not be considered for determination of a PFS event, unless the outcome of the progression is death.

If patients would have their radiological examinations over a number of days, i.e. target lesions assessed on day x, non-target lesions assessed on day y and new lesion (if applicable) on day z, the following rules will be applied:

- If the overall response is PD, the earliest date of multiple assessments will be taken.
- If the overall response is SD, Non-CR/Non-PD, PR, CR or NE, the latest of multiple assessment dates will be taken to censor the patients.

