7.5.2.2 Cohorts E and F, D1 and D2

Disease control (Cohorts E, D1 and D2 only)

Disease control (DC) is defined as best overall response of complete response (CR) or partial response (PR) or stable disease (SD) (defined in [Section 5.2.2.2](#)). Only descriptive statistics are planned for this section of the report.

Time to OR

For patients with objective response, time to objective response will be shown on patient level. A set of summary statistics for time to objective response on cohort level will also be produced.

Duration of OR

KM estimates will be calculated for each treatment group to provide estimates of the median, 25th and 75th percentiles and their corresponding 95% CIs.

Duration of DC

Duration of DC will be analysed similarly to Duration of OR, see above.

Progression free survival

[figure not shown]
Kaplan-Meier estimates and 95% CIs (based on Greenwood's method) will be calculated. Furthermore progression free survival times on patient level will be shown and if applicable descriptive statistics including, but not limited to, the lower quartile (P25), Median and the upper quartile (P75) will be computed.

Objective response (Cohorts F, D1 and D2 only)

[figure not shown]
OR as assessed by investigators is defined as a best overall response of CR or PR and will be analysed. Descriptive statistics including number of treated patients, number of patients with

Proprietary confidential information © 2021 Boehringer Ingelheim International GmbH or one or more of its affiliated companies

objective response as best overall response and the corresponding percentages will be presented and evaluated.

Proprietary confidential information © 2021 Boehringer Ingelheim International GmbH or one or more of its affiliated companies

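### For cohorts D1 and D2 the SAP gives the primary endpoint's name to a percentage of treated patients that censoring pulls downward, while the protocol's Kaplan-Meier rate at 18 months is left as support for a plot

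*SAP*

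**What the plan says.** Protocol 5.1.1 makes the PFS rate at 18 months the primary endpoint for D1 and D2, and protocol 7.3.1 fixes the method: "PFS rate at 18th month will be derived using Kaplan Meier method". It leaves the details to the SAP. Protocol 3.2 uses looser language, with "PFS18 defined as the proportion of patients who were absence of disease progression or death at 18th month", and names no estimator.

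SAP 5.1.3 defines the endpoint at patient level: "PFS18 is defined as the PFS status of a patient who is alive without disease progression at 18 months after first treatment administration". SAP 7.4.3 then gives the number of treated patients and the "number of patients being absence of disease progression or death at 18th month and the corresponding percentages will be presented and evaluated". The Kaplan-Meier curve follows in the same section, with this role for the 18-month estimate: "To support the plot, estimated survival probabilities at specific time points of interest (6 months, 12 months and 18 months) will be tabulated".

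Two general rules bear on the percentage. SAP 6.3 says "The TS will be used for all planned safety and efficacy analyses", where TS is the treated set. SAP 7 says "Percentages will also generally be based on all patients in the respective patient set whether they have non-missing values or not". For PFS as a secondary endpoint, SAP 7.5.2.2 says "Kaplan-Meier estimates and 95% CIs (based on Greenwood's method) will be calculated". SAP 4.2, which lists changes from the protocol, has no entry.

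**The concern.** A Kaplan-Meier rate and a simple percentage agree only if every patient is followed to progression, death or month 18. SAP Table 5.1.3:1 censors patients who start new anti-cancer therapy, miss two or more consecutive scans, or have no post-baseline scan. Protocol 7.7 plans for 20% drop-out. The D1/D2 primary-endpoint milestone in protocol 8.6 can be met by patients who have permanently stopped treatment, so the data may include patients not observed to month 18.

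The scan calendar adds to this. By the conversion in SAP 7, 18 months is 18 × 365.25 / 12 = day 548. That lies between the week-72 scan (72 × 7 + 1 = day 505) and the week-84 scan (day 589). A progression-free patient whose last scan is at week 72 is censored before month 18.

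The SAP does not say how such a patient enters the PFS18 percentage. PFS18 success requires being alive and progression-free at 18 months, and the treated set is the denominator whether or not the value is known. Read together, a patient censored early counts as a failure. These are single-arm descriptive cohorts, so the estimate is the result. Readers will set the figure named PFS18 against the planning values of 60% and 69% and the reference values of 43% and 52%.

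**Working it through.** **Inputs from protocol 7.7.** n = 30 per cohort. D1: assumed true rate 60%, reference 43%, threshold above 57%. D2: assumed true rate 69%, reference 52%, threshold above 65%. Drop-out 20%, with no stated time base.

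**Assumptions not in the documents.** Exponential PFS through the stated 18-month rate; independent drop-out, with share d lost by month 18.

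**Step 1: reproduce the protocol's figures.** Simulated trials (40,000 per setting) with Kaplan-Meier at month 18 and d = 20%:

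| Cohort, true rate | Protocol | Kaplan-Meier | Mean estimate |
|---|---|---|---|
| D1, 60% | 0.62 | 0.63 | 0.600 |
| D1, 43% | 0.08 | 0.075 | 0.43 |
| D2, 69% | 0.68 | 0.68 | 0.690 |
| D2, 52% | 0.10 | 0.09 | 0.52 |

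A normal approximation with 24 evaluable patients also comes close (0.618, 0.083, 0.664, 0.101), so the tables do not identify Kaplan-Meier uniquely.

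**Step 2: the treated-set percentage.** A patient is a success only if progression-free and still under observation at month 18. The expected percentage is S(18) × (1 − d), and the count is binomial(30, S(18) × (1 − d)). Exceeding 57% needs at least 18 of 30 (17/30 = 56.7%). Exceeding 65% needs at least 20 of 30 (19/30 = 63.3%).

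| Drop-out by month 18 | D1 expected | D1 P(>57%) | D2 expected | D2 P(>65%) |
|---|---|---|---|---|
| 0% | 60% | 0.58 | 69% | 0.69 |
| 5% | 57% | 0.44 | 66% | 0.53 |
| 10% | 54% | 0.32 | 62% | 0.38 |
| 20% | 0.60 × 0.80 = 48% | 0.13 | 0.69 × 0.80 = 55% | 0.14 |
| 30% | 42% | 0.04 | 48% | 0.03 |

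At 20% drop-out and the reference rates, the chances are 0.004 (D1) and 0.005 (D2), against the stated 0.08 and 0.10.

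**Step 3: other ways to treat censored patients.** With exponential drop-out, the share censored before month 18 is m/(l + m) × (1 − S(18) × (1 − d)), where l = −ln S(18) and m = −ln(1 − d).

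- D1 at 20%: 0.2231/(0.5108 + 0.2231) × 0.52 = 0.158, or 4.7 of 30 patients.
- D2 at 20%: 0.2231/(0.3711 + 0.2231) × 0.448 = 0.168, or 5.0 of 30 patients.

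Dropping them from the denominator gives about 0.48/0.842 = 0.57 in D1 and 0.552/0.832 = 0.66 in D2, with exceedance chances of 0.51 and 0.58. Counting them as progression-free gives 0.48 + 0.158 = 0.64 and 0.552 + 0.168 = 0.72, an upward bias. No handling of the simple percentage recovers 0.60 and 0.69.

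**The case against.** **Nothing is lost.** The 18-month Kaplan-Meier probability is tabulated by cohort inside SAP 7.4.3, under the PFS18 heading, and Greenwood intervals are planned for PFS. The SAP never ranks the two outputs explicitly. This is correct, and it limits the repair to naming. But the SAP's PFS18 definition leads straight to the count and percentage, while the Kaplan-Meier value is introduced as support for a plot.

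**The proportion wording began in the protocol.** Protocol 3.2 does call PFS18 a proportion, and 7.3.1 defers details to the SAP. The SAP can therefore claim to deliver both. However, 3.2 gives no method and 7.3.1 does, and a different estimator is more than a detail.

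**The downward direction is inferred.** The SAP has no explicit rule for censored patients, and its denominator statement is qualified as general. It also provides for a missing category and for censored counts in its tables, so readers may see some of the uncertainty. Counting censored patients as successes would push the figure upward. This stands as a caution, but the failure reading follows most naturally from the definition and the denominator rules together.

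**The size depends on assumptions.** The 20% has no time base. D1/D2 patients who stop treatment without progression stay in follow-up for progression, so stopping treatment does not itself censor. At 5% drop-out the shift is only about 3 points. Part of the fall in D1 is granularity: with no drop-out the chance is already 0.58 rather than 0.62, and counting 17/30 as 57% gives 0.22 instead of 0.13 at 20%. Kaplan-Meier is itself unbiased only if censoring is independent, and censoring at new therapy may not be. All of this is fair; it moves the size but does not make the two figures equal.

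**No decision rule depends on it.** Protocol 7.2 plans no formal test, and the 7.7 thresholds illustrate precision. This limits the harm to the reported estimate.

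**Conclusion.** The concern holds and should be fixed. Followed as written, the SAP attaches the primary endpoint's name to a figure that departs from the method in protocol 7.3.1 and, on the natural reading of its own rules, falls below the true rate whenever patients are censored before month 18.

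At 20% independent drop-out by month 18 the shortfall is 12 points in D1 (48% against 60%) and 14 points in D2 (55% against 69%). A regimen performing as hoped would then read close to the 43% and 52% reference rates. At 5% drop-out the shortfall is about 3 points, and with no early censoring it disappears. The protocol's stated probabilities describe the Kaplan-Meier figure and do not describe this percentage.

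These sizes rest on exponential PFS and on the assumed timing and independence of drop-out. The mismatch between the two documents does not depend on those assumptions. Confidence is high.

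**What to change.** - In SAP 5.1.3 and 7.4.3, name the 18-month Kaplan-Meier PFS probability, by cohort and with the Greenwood-based 95% CI already planned in SAP 7.5.2.2, as the primary PFS18 estimate.
- Keep the count as supportive only, split three ways: progressed or died by 18 months, known progression-free at 18 months, and censored before 18 months.
- Align protocol 3.2 with protocol 7.3.1.
- If the sponsor prefers the percentage as primary, declare that in SAP 4.2 with an explicit rule for patients censored before month 18.

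The main change is wording only, because the 18-month estimate and the Greenwood intervals are already planned outputs. The three-way split is one small extra table per cohort.
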